For the **Focus group** respondent burden will be participation in a 3 to 3.5 hour group where they will view and return demonstration of use of the smart phone and LN mobile app and provide feedback both written and verbal. For the **RCT** participants will be in the study about 10 months, and will be asked to listen to and use the LN mobile app during that time. They participate in 4 computer interviews that are around 3 hours each, and provide 100 strands of hair at each interview. They will also participate in monthly unannounced pill counts via mobile app or telephone call.

e. Measures

Behavioral measures will include: 1) assessments of adherence to antiretroviral medications; 2) measures of symptoms, depression, self-efficacy, attitudes, goals, demographic information including substance use, and health literacy; and 3) smartphone app acceptance and usage measures, along with eHealth literacy and smartphone experience. Physiologic measures will include ART drug levels in a small hair sample (100 strands) cut from the occiput (back of head) at each time point. Lab results for CD4, viral load, and drug resistance will be extracted from medical records consistent with the study time points. Usage tracking will be captured via the previously mentioned mobile web application, which will transmit messages to the HIPAA compliant server each time a participant uses the app. A table with a list of measures and copies of each instrument is uploaded into the IRB application.

f. Risks to participation

f.1 For **Focus groups** there is a risk of breach of confidentiality when persons come together in a group format. The risks include identification/disclosure as HIV+ to others in the group and discussion of

private information outside the group. There is a remote risk of anxiety or stress related to the discussion content. For the **RCT** there is a very remote risk of injury from clipping hair samples. Completion of the assessments and participation in the interventions are free of risks for physical harm. However, both the assessments and the intervention may raise personal issues, which may be troublesome to some of the participants. Some participants may feel anxious as a result of dealing with these issues. Use of the mobile app and text messaging could display private information. These risks will be explained in the consent form. All study staff will be trained in the mental health aspects of HIV/AIDS, how to recognize and deal with emotional or behavioral problems, including anxiety, as they arise, and will be asked to report all adverse events to the principal investigator.

f.2 Procedures to reduce Risk

f.2.a. Recruitment and Consent Procedures

Men and women who meet the study criteria will be recruited at the HIV Clinics described above. Site coordinators will be trained to deliver a presentation briefly explaining the study and answering questions about the study. Potential participants will receive written materials about the study and will be given a phone number to call. Individuals who are interested in participating will be given a screening assessment to assess eligibility. Before the screening assessment, the study will be explained in detail including the purpose of the study, the participant's role in the study, study requirements, and time commitments, confidentiality and privacy protections (including for focus groups and RCT), and questions will be answered. Potential participants will be assured that their care at the clinic will not be affected in any way by their decision whether or not to participate in the study. They will be given an opportunity to ask questions and receive additional explanation. The consent form includes an explanation of the study, the risks and benefits of participation, the duration and type of participation, description of the procedures, contact person for the research including the chair of the IRB, the voluntary nature of participation, and the right to withdraw without penalty will be read and explained. Since this population is at risk for cognitive impairment that, in some cases, may limit capacity to provide consent, a consent post-test will be administered to evaluate understanding of study procedures, risk/benefits, etc. If this is completed with 100% accuracy, they will be asked to sign an informed consent form, and given a copy of the form for their records. For focus groups, the group will begin thereafter. For the RCT, they will next complete the BSI screening and if the results of the screening assessment indicate that they are eligible for the study, they will be given an invitation to participate. They will then begin the baseline assessment.

f.2.b. Protections Against Risks

To minimize the risks associated with clipping hair, we will train and check off each site coordinator, and establish reliability between and within coordinators in their ability to follow established protocols consistently. In addition to the above procedures regarding possible mental health risks, using a coding system for tracking assessments will minimize threats to confidentiality. All confidential information including code numbers and data will be kept in a locked office in locked file cabinets with limited access. Names will never be linked with data. All study data will be kept on a secure password protected, HIPAA-compliant server at Emory University. Flash videos associated with the music program will not display terms such as HIV/AIDS that could disclose status. We will encourage use of the interactive manual, which will contain specific HIV related information, in a private area. Any text messages sent will not contain private information or terms that may disclose status. Code words will be used when needed to send reminders to use the app, and for assessments, pill counts. When calling participants, we will always ask if they can talk privately and if not, set a time to call back. The project name "Music for Health Project" does not contain terms that could be associated with HIV/AIDS. LN and EP usage data will be tracked on a HIPAA-compliant secure server at Emory University.

To ensure that information discussed in all focus group sessions is kept confidential, a reminder contract will be read at the beginning of every session. This verbal contract will emphasize that each participant is responsible, as are the staff, for not discussing information outside of the room and not disclosing participant names or identities to others outside the room. Only first names will be used in all focus groups. Digital audio recordings used for data collection for focus groups will be labeled by a group number and date. These will be kept in on a secure server with limited password protected access. The transcriptionist will follow a strict check out and confidentiality procedure for transcribing recordings; no names/identifiers will be used when transcribing, analyzing, or reporting the data. In addition to the above procedures regarding the slight possibility of emotional response or anxiety, all our staff are trained to provide emotional support to anxious or stressed out participants. We have an established protocol for mental health referrals and there is an existing mental health referral system at each site, which we will use if needed. Participants will be informed they may stop participation if it is stressful to them.

In order to main confidentiality, all study staff and site coordinators will be required to sign a confidentiality statement.

g. Benefits to subject or future benefits

The benefits of our intervention include learning about antiretroviral medications, ways to enhance adherence, ways to problem solve and develop personal strategies for taking ART consistently, ways to self-manage symptoms, and receipt of the incentives to promote retention in the project. We believe that the benefits of the intervention outweigh the possible negative consequences.

h. Data analysis

h.1 Rationale for proposed number of subjects and sample calculations

The target sample size is 200 participants with 100 allocated to each group. Taking into account projected attrition of about 40 persons, we expect a final sample size of 240. Given our approach using multi-level longitudinal models (MLM) for these 200 subjects, 2 groups at 4 time points, we are 95% confident that power levels between 84% to 98% will achieve minimal detectable differences of 0.4 (within time and group by time) and 0.5 (between groups) (small-to-moderate effect sizes) for random effects subjects variance equal to 1. Covariate adjustments should further reduce variability and detectable effect sizes while increasing power. Additionally, to address the differences in proportion achieving virologic suppression and drug resistance, a chi-square test for a sample size of 200 yields a small-to moderate effect size (ω) of 0.1981 for 1 degree of freedom (2 x 2 table) at 80% power and 5% level of significance.

h.2 Plans for data management and analysis

h.2.a Data management Procedures for data management and monitoring will be initiated during the start-up phase. The project coordinator will coordinate the organization and processing of forms, and schedule and implement checks of data quality and completeness. Data from the ACASI files will be saved in the QDS data warehouse. Data will be backed up on a regular basis to prevent loss of data. Data will be transferred electronically from the sites to a secure password protected, HIPAA-compliant server at Emory University. A data-checking plan based on each questionnaire will be used to look for suspicious entries. Data monitoring will include scheduled checks for completeness every 2-4 weeks. Data sets from all assessment points will be merged as necessary to answer the research questions. Personal goals will be reported by the participant and typed into the database for qualitative analysis. They will be analyzed for the dimensions of content, specificity, effectiveness, and control. [name] will oversee the final quality assurance/quality control data reviews. She will design and conduct the statistical analyses; assist as with designing research forms and data entry; and collaborate with the

investigators on analysis and interpretation. We have successfully used these procedures with the pilot project and other research projects.

h.2.b Analysis Initial analysis will include descriptive statistics of sample characteristics (demographics, substance use, depression scores, etc. and CD4 and Viral Load.) and psychometric evaluation of all scored instruments. A combination of statistical software will be used for statistical analysis and data visualization, including SPSS (v.19), SAS (v. 9.2), and R (v. 2.13). Distributions, potential outliers, and patterns of missing data will be assessed to assure that the data meet assumptions for subsequent inferential tests. Missing data imputation methods may be used for small amounts (<5%) of missing data such that missing data are random. All statistical tests will be performed at the 5% level of significance, with exact p-values reported. Intent-to-treat procedures will be employed. For non-normal data, transformations may be performed to improve deviations from normality. However, it is well known that PC, viral loads and adherence measures are often skewed and experience floor and/or ceiling effects. Therefore, generalized linear models (GLM)/generalized estimating equations (GEE) frameworks will be employed as a more accurate reflection of the true underlying distributions generating these data. It is expected that logistic (logit)³⁷ and log-gamma³⁸ may be appropriate as well as Poisson, zero-inflated Poisson, and other link functions.^{39, 40} Additionally, it is expected that some attrition over time will occur. Mixed/multi-level models (MLM) will be used instead of repeated measures analysis of variance (RM-ANOVA) methods since MLM uses all available data (does not delete cases with missing values over time), handles data that are missing at random (MAR) which RM-ANOVA cannot, does not assume independence across time, provides a breakdown of variance both within and between subjects, and allows for both time-invariant and time-varying covariates.^{39, 40} It is expected that the majority of the analyses will occur in SPSS. However additional MLM and GLM/GEE models will be run using SAS (PROC MIXED, PROC NLINMIXED) and R (packages: LME4, GAMLSS as well as BRugs, which employs Bayesian estimation methods.⁴¹⁻⁴³

Satisfaction (Aim 1) Two assessments will be conducted and analyzed to determine participant satisfaction with the mobile app in general, LN program and interactive manual. Both times, we will ask questions about likeability, usage rates, ease of use, acceptability, satisfaction, relevance, favorite song, understandability, and suggestions for improvement. The first assessment will entail observations and discussions with rural PLWHA while using the mobile app in focus group format. Observations and discussions will be recorded and content analyzed for themes, which will inform final revisions to the LN app. The second feasibility analysis will be the Program Evaluation Survey at the end of the study. Scaled responses to questions related to the above criteria will be analyzed using descriptive statistics and written comments will be entered into nVivo software and content analyzed for themes. We will also describe and evaluate the usage data from the web application designed to track app usage. We will determine average usage patterns and compare between groups (LN vs. EP).

Outcomes (Aim 2) All covariates will be evaluated to determine if any differences exist at baseline between the 2 groups (LN and EP), as well as testing for interactions (moderation) between groups and time. Inter-correlation among the covariates will also be evaluated. Multicollinearity diagnostics (variance inflation factors, tolerance, condition index) will be used to determine which covariates should remain in the subsequent models. MLM longitudinal models as detailed above will be used for each outcome (H1: adherence, H2: drug levels, and H3: CD4, viral load, drug resistance) to test differences between the 2 groups (group main effect), test for changes/differences from baseline to 3, 6 and 9 month (time main effect) and test for group by time effects (i.e. changes from baseline that are differences between the 2 groups) adjusting for significant covariates/moderators as needed. Appropriate link functions (e.g. logit, Poisson, other) will be assessed for each outcome within the MLM.

Exploratory outcome, mediators and moderators (Aim 3) Symptoms and symptom management scores will be examined using MLM as described above. Self-efficacy, outcome expectancy and personal goals are mediators in our model and meet the criteria for mediators as defined by Baron and Kenny⁴⁴

and Bennett.⁴⁵ First, the intervention is designed to foster change in self-efficacy, outcome expectancy, and personal goals, and second, the mediators, in turn, are associated with the outcomes of adherence and symptoms. A number of authors have explicated the process by which mediation can be tested.^{46,47} A combination of statistical methods will be employed to determine the significance of mediation effects through the SPSS macro as described in Preacher and Hayes.⁴⁸ This SPSS macro runs the Baron and Kenny method and Sobel⁴⁷ test, as well as a non-parametric bootstrapping estimate, which is a more rigorous alternative to the Sobel test of the indirect effects. Based on the outcomes of these tests, each potential mediator will be assessed as to whether it provides for total, partial, or no mediation effect. Moderators such as depression and health literacy will be tested for main effects (differences at baseline) as well as for interaction (moderation effect) with the intervention (group) and across time. These moderation effects will be included within all mediation models to assess the extent of mediation of self-efficacy and outcome expectancy on adherence outcomes after adjusting for moderators and covariates.

Smartphone acceptance (Aim 4) Multivariate regression models will be used to address each hypothesis related to this aim. For Hypothesis 1, each antecedent (effort expectancy, performance expectancy and hedonic motivation) will be tested as a significant predictor of behavioral intent after adjusting for potential demographic covariates, such as age and gender. For Hypothesis 2, a simple regression model will assess the amount of association between behavioral intent and LN/EP app usage. For Hypothesis 3, multivariate regression will again be used to test for the moderating effects (i.e. two-way interaction effects) of smartphone experience and eHealth literacy on the association between the antecedents and behavioral intent. In place of traditional regression methods, the PROCESS plug-in macro for SPSS⁴⁹ will be employed using methods outlined by Hayes⁵⁰ to test the moderation effects of both smartphone experience and eHealth literacy on behavioral intention. (Note: for a continuous predictor variable and a continuous moderator variable, each will be mean-centered using the PROCESS macro before computing the interaction variable to avoid mathematically induced multicollinearity issues present for moderation testing.)

Exploratory outcome (Aim 5) Analysis includes the first 106 participants in the main study and participants are compared based on their inclusion criteria (participants switching ART medications because of new resistance (non-adherence) vs those starting or switching ART medication for non resistance reasons or toxicity). Data will be de-identified by the Rural Music Project data manager prior to analysis. The data manager will not conduct any data analysis for this aim. Baseline ACASI data will be merged with inclusion criteria data from site tracking log based on the participant identification number and analyzed using SAS (v. 9.4) statistical software.

3. Training research personnel

Interviewer training Experienced interviewers will be trained to conduct baseline and follow-up interviews. To control for measurement error, we will be using ACASI to administer most of the items. Interviewers will also be trained in hair sample collection, processing, and storage. This process will be standardized based on the equipment and procedures. We will develop procedures manual which includes all the important elements of interviewing along with specific information related to each item on the questionnaires/surveys, as well as written procedures for hair sample collection, processing, and storage. This manual will serve as the basis for training. Interviewers will use standardized scripts to introduce the participant to the study and explain the questionnaires/surveys, and procedures. The interviewers will practice the survey, screening, baseline, and follow-up scripts with each other. They will practice hair-sampling procedures on models. Weekly meetings and contact with the PI will be held to discuss problems and issues that may arise.

Focus group facilitator training Two focus group facilitators will conduct the groups. They will be trained in group dynamics and how to ask general questions and more specific questions. They will use a script written by the PI and Co-I to elicit comments about the LN app and smart phone use.

4. Plans for data management and monitoring

As mentioned above the potential risks from this study are minimal and we had no adverse events during the pilot study of the Music Project (n = 77). Therefore, adverse events and clinical outcomes will be monitored by the Principal Investigator (PI) in collaboration with the Co-Investigators (Co-I's). All study staff will be trained to recognize and report adverse events immediately to the PI who will report them to the Emory University IRB. Data management will be done by the study project coordinator who will assure quality and security of the data from start through conclusion of the project and will notify the PI of any breaches in data security. S/He will also provide real-time checks of forms-based data, and at least monthly monitoring of data quality and completeness.

The PI will review the following indicators on a monthly basis.

- a. adherence to the goals for recruitment and retention;
- b. adherence to the study protocols;
- c. cumulative data for evidence of study related adverse events;
- d. quality, accuracy, completeness, and timeliness of the data collected thus far;
- e. factors that could affect the outcome or compromise participant/data confidentiality;
- f. other factors outside the study (e.g., therapeutic developments, agency related policies) that could impact the safety of participants or the ethical conduct of the study.

In general, if problems arise, the PI will consult with Co-I's and the IRB to make possible recommendations:

- a. continue the study without change;
- b. modifications to the study protocol;
- c. suspension or early termination;
- d. alternative approaches to consider (e.g., if there is a failure to accrue participants as anticipated, such as addition of another site).

If a breach in data or individual confidentiality, a study related adverse event, or a significant protocol violation occurs, the PI will contact the IRB as soon as possible to discuss and make recommendations for action.

5. Confidentiality

See 'F' above.

6. Informed consent

The informed consent for each part of the study has been downloaded to the e-IRB application.

Individuals who are interested in participating will be given a screening assessment to assess eligibility. Before the screening assessment, the study will be explained in detail including the purpose of the study, the participant's role in the study, study requirements, and time commitments (including for the intervention and assessments), and questions will be answered. Potential participants will be assured that their care at the agency will not be affected in any way by their decision whether or not to participate in the study. They will be given an opportunity to ask questions and receive additional explanation before signing the appropriate consent form which includes an explanation of the study, the risks and benefits of participation, the duration and type of participation, description of the procedures,

contact person for the research including the chair of the IRB, the voluntary nature of participation, and the right to withdraw without penalty. If interested, they will be asked to sign an informed consent form and will be given a copy of the form for their records.

7. Plans to inform participants of new findings or research results that might affect health

The following statement has been added to the consent form for the main pilot study.

New Findings: If significant findings are found during this research, this information will be provided to you.

8. References

1. Centers for Disease Control and Prevention *HIV/AIDS surveillance in urban and nonurban areas (through 2008)*; 2010,
2. Kaiser Family Foundation *Estimated Rates (per 100,000) of AIDS Diagnoses, All Ages*; 2010,
3. Georgia Department of Community Health *Fact Sheet: HIV/AIDS Surveillance; April 2011*; 2011,
5. Krawczyk, C. S.; Funkhouser, E.; Kilby, J. M.; Vermund, S. H., Delayed access to HIV diagnosis and care: Special concerns for the Southern United States. *AIDS care* **2006**, 18 Suppl 1 S35-44, PMID: 16938673.

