We conducted a pilot RCT at the same site to compare the program with usual care (at least 2 visits with a Nurse Educator). We enrolled 77 persons who started or changed ART within the previous 6 months. Participants were randomized 2:1 to LN (n = 51) or standard care (n = 26) and completed baseline (T1), 6 week (T2), and 12 week (T3) assessments and monthly pill counts (PC). Blood draws measured plasma antiretroviral medication trough levels at 12 weeks, an innovative measure of adherence. Significance for this small sample pilot was set at $p \leq .1$. Mean age was 44.7 yrs; 65% were male; 88% were African American; participants were HIV-infected for 9.6 years (median). Median monthly income was \$674. At T3 we found adherence declined over time for both groups; however the drop was greater for the control group compared to the LN group: 67% (14 of 21) of controls but only 52% (22 of 42) of intervention subjects dropped below baseline values (NS). While not statistically significant, PCs at T3 were higher for intervention participants (77.8% vs. 70.6%). Also at T3, 80.5% of LN subjects vs. 72.7% of controls had antiretroviral plasma trough levels at or above therapeutic range (n=63, NS). CD4 and viral load (VL) were analyzed using multilevel mixed models. There was a larger proportion of LN group with undetectable VL log (≤ 1.88) at all time points. VL log (inverse transformed) yielded a significant group by time interaction ($t=1.890$, $p=0.067$, and model deviance change $\chi^2=3.07$, $df=1$, $p=0.08$) for the LN. No significant differences were seen for CD4. Adherence self-efficacy scores improved in the LN group from T1 to T3 ($\chi^2=5.1$, $df=2$, $p=0.080$). No significant changes were seen for the control group ($\chi^2=2.6$ ($df=2$), $p=0.273$). Wilcoxon pairwise post hoc tests using Bonferroni corrected alpha=0.033 indicated significant differences between T1 and T3 ($Z=-2.39$, $p=0.017$) and between T2 and T3 ($Z=-2.39$, $p=0.017$). Self-efficacy had the largest effect sizes seen in this study; the largest changes occurred between T1 and T3 indicating that the study should be run longer to establish sustainable improvements. For the LN group, ART self-efficacy scores increased by 6.05 ($sd=12.97$) for an estimated effect size of 0.47, a medium effect size. Participants with higher CES-D scores (depressive symptoms) at T1 were 1.08 times more likely ($p=0.03$) to have drug trough levels below the therapeutic range at T3. There were no differences between or within groups in numbers of symptoms or symptom distress. Small sample size and short duration of follow-up limit our results. All

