
measures of adherence were subject to bias: patients can dump pills prior to PC, as well as "load" medications prior to blood level testing. We feel these are encouraging trends in adherence, VL, and self-efficacy. Measuring adherence using therapeutic drug levels was innovative, easy to collect, and enhanced the objectivity of the findings. These results were presented at the Association of Nurses in AIDS Care annual meeting in November, 2010. LN program evaluation: LN participants completed an evaluation rating satisfaction, likability, usage, and suggestions for improvement at the end of the study. 47 of 51 LN participants completed the evaluation and expressed overwhelmingly positive responses to the questions. The following are the percentage of persons who agreed or strongly agreed with the items: 87% liked the DJ segments, 83% liked the music styles, and 87% reported the lyrics were easy to understand. For the manual, 91.5% felt it was easy to use, 89.6% felt it was understandable, and 89.1% liked it and felt it was helpful. On a scale from 'none' to 'greater than 10 times', 17% reported listening to the songs 5 to 10 times and 42% reported listening >10 times in the prior 3 months. 42% reported listening to the DJ segments 1-5 times and 29% listened >10 times. Overall the manual was used less than the songs; 12.5% reported not using the manual at all; 37.5% used it 1-5 times; only 23% used it >10 times in the prior 3 months. Participants rated each song and manual section on a 0 (hated it) to 10 (loved it) scale. Every song and all but one manual section received mean ratings over 8.5. The lowest mean song rating was for It Ain't Easy at 8.6 and the highest mean ratings were That's My Motivation and You Can Work it Out, both at 9. The lowest rated manual sections were Stress and Depression at 7.71 and Symptoms and Side Effects and Disclosure, both at 8.54. The highest rated manual sections were Your Support Team (9.37), Adjusting to Taking ART Medications (9.18), and Goal Setting (9.16). Regarding the 800 number, 47% reported not using it, probably because the clinic was easily accessible and patients preferred to come in or call the study office with questions. Overall, only a few participants made suggestions for changes to the LN. One person wanted more jazz, 2 wanted more songs, 1 said the music style was too young, and 3 felt the manual was too large.

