RCT: Inclusion criteria for the study are: 1) HIV infection; 2) initiating ART for the first time (except women who may have had ART during pregnancy) or changing ART regimen within the past 3 months due to side effects or virologic resistance; or 3) HIV+ individuals with a detectable viral load \geq 40copies/ml; 4) HIV+ individuals on ART medication 5) \geq 18 years of age; 6) English speaking; and 7) willing to complete 4 assessments, monthly unannounced pill counts, and collection of hair samples, be randomly assigned to either condition, and participate in study activities that include using smart phone and mobile app. Persons will be excluded from the study if they are not HIV infected, homeless, are a minor under 18 years of age and therefore unable to give independent informed consent, are unable to read or understand English since all of the questionnaires and the audio program and manual will be in English, have a history of or self-report bilateral hearing loss, cognitive impairment (inability to comprehend the informed consent document), are actively psychotic, severely depressed/suicidal, or pose a risk of harm to themselves or others (Brief Symptom Inventory; BSI), since these persons may not be capable of using the mobile app or completing the assessments. Depending on the severity, these persons will be walked to or referred to the mental health counselor, once the mental health issues have been addressed, they may be re-screened for eligibility. Substance users will not be excluded from the study, except if they display the above mentioned mental health characteristics or pose a risk of harm to themselves or others.

b. Setting

The study sites are within 5 health district sites that provide care to HIV+ persons in rural counties in Georgia outside the 20-county Metropolitan Atlanta Statistical area (MSA). The sites of the project are:

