RCT: Sources of information will include baseline, 3, 6, and 9- month follow-up assessments and tracking of usage of mobile app conducted solely for the purpose of this research. Assessments will include assessments of adherence to antiretroviral medications and, measures of symptoms, depression, self-efficacy, attitudes, goals, demographic information including substance use, and health literacy. Physiologic measures will include ART drug levels in a small hair sample (100 strands) cut from the occiput (back of head) at each time point. Lab results for CD4, viral load, and drug resistance will be extracted from medical records consistent with the study time points. Study assessments will be conducted in person using ACASI coincident with provider appointments. They will last about 3 hours. Monthly unannounced pill counts will be conducted via smart phone using the camera and pill count survey within app with assistance from the clinical research coordinator as needed. As part of our reliability testing, up to 60 participants will be asked to repeat their pill count about 24 hours after baseline. Hair samples will be collected in person by study personnel on-site at each time point. Tracking usage of the app will be done via the mobile web application which will send messages to the HIPAA compliant server each time a participant uses the app. Participants will be assigned to one of two conditions: an educational music program (EP) or the LN treatment condition. All participants will receive the usual care at their respective HIV care agencies. Evaluation information will be obtained about the satisfaction and use of the programs at the end of the RCT study. The option of 3, 6, and 9 month follow up study assessments administered via phone call will be offered to participants who are unable to complete in person visits. If this option is elected the hair sample and visual analog scale data will not be collected.

d.1.b Other interactions

Participants will receive reminder calls and text messages regarding study appointments. Text messages will also remind them to listen to the LN & EP.

d.2 Respondent burden

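### Does a confidentiality sentence about coded messages undo the unannounced monthly pill counts?

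*Combined protocol and SAP*

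**What the plan says.** Three sections of the protocol describe the monthly counts in the same way.

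- The RCT inclusion criteria (a.2) require that participants be "willing to complete 4 assessments, monthly unannounced pill counts, and collection of hair samples".
- The data collection procedures (d.2.1) state: "Monthly unannounced pill counts will be conducted via smart phone using the camera and pill count survey within app".
- The respondent burden section adds a telephone mode: "They will also participate in monthly unannounced pill counts via mobile app or telephone call".

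Two sentences under Protections Against Risks (f.2.b) bear on the timing of contact. One is "Code words will be used when needed to send reminders to use the app, and for assessments, pill counts". The other, on telephone contact in general, is "When calling participants, we will always ask if they can talk privately and if not, set a time to call back".

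The section on other interactions (d.1.b) describes the reminders that participants get: "Participants will receive reminder calls and text messages regarding study appointments", plus texts to listen to the assigned program (Live Network, LN, or the educational control, EP). Pill counts are not on that list.

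**The concern.** Pill counts are one of the two adherence measures named in H1; the other is self report. Of the pilot, the investigators write that all "measures of adherence were subject to bias: patients can dump pills prior to PC". A count without warning is the step described in the protocol that works against this, because a camera shows the pills that remain and not those thrown away.

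The f.2.b sentence puts pill counts beside assessments, which coincide with clinic appointments and do get advance reminders. A site coordinator could take it to mean that counts are also announced. The call-back rule could have a similar effect for a count done by telephone, since a participant who is given a time might guess the purpose. If counts were announced, recorded adherence could rise in both arms, the expected ceiling effects could worsen, and the LN-EP difference in percentage points could shrink.

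**Working it through.** No planned figure depends on this point, so the main check is a reading of the sections against each other.

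**1. What the coded-message sentence governs.** It can be read in three ways:

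- (a) advance reminders for app use, assessments and pill counts;
- (b) code words in any message about a pill count, including the prompt that starts it;
- (c) code words for two separate purposes: reminders to use the app, and contacts about assessments and pill counts. The comma after the word app allows this.

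Only (a) conflicts with the three statements that counts are unannounced. Readings (b) and (c) agree with all of them. An app-based count also needs some message to start it, so a coded message about a count is necessary even when nothing is announced.

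**2. What the surrounding text is about.** The neighbouring sentences in f.2.b deal with keeping private information out of texts, the neutral project name and speaking privately on calls. They do not set a message schedule. The section that does describe reminders (d.1.b) leaves pill counts out.

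**3. A count that may properly be announced.** Under d.2.1, up to 60 participants repeat their pill count about 24 hours after baseline for reliability. That count is planned by design, and a reminder for it contradicts nothing.

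**4. The call-back rule.** Staff first ask whether the participant can talk privately. Nothing says that they disclose the purpose of the call before privacy is confirmed, so an agreed call-back need not reveal that a count is due. The rule reaches pill counts only through the telephone mode.

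**5. Size, as an illustration only.** Inputs: the pilot pill-count means at T3, 77.8% for LN and 70.6% for usual care (Preliminary Studies), a gap of 77.8 − 70.6 = 7.2 points. Assumption: a share *h* of missed pills is discarded before every count, equally in both arms.

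Observed adherence = 100 − (1 − *h*)(100 − true adherence), so the observed gap = (1 − *h*) × 7.2.

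| *h* (assumed) | LN | Control | Gap (points) |
|---|---|---|---|
| 0 | 77.8 | 70.6 | 7.2 |
| 0.1 | 100 − 0.9 × 22.2 = 80.02 | 100 − 0.9 × 29.4 = 73.54 | 6.48 |
| 0.3 | 100 − 0.7 × 22.2 = 84.46 | 100 − 0.7 × 29.4 = 79.42 | 5.04 |
| 0.5 | 100 − 0.5 × 22.2 = 88.90 | 100 − 0.5 × 29.4 = 85.30 | 3.60 |

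If *h* is the same for everyone, each person's shortfall from 100 is multiplied by (1 − *h*), and so is the standard deviation. The standardised difference is then (1 − *h*)Δ / ((1 − *h*)σ) = Δ/σ, which is unchanged. The documents give no standard deviation for adherence, so no loss of power can be derived.

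**The case for a change.** The strongest case for a change is that the wording is loose and would be cheap to tidy. Locally hired coordinators run all study activities at each site and might apply the sentence differently. No section says when a pill-count message goes out, how long the participant has to respond, or how a rescheduled count is recorded. Hair drug levels are a separate outcome (H2) and do not correct a distorted count.

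The looseness and the missing detail stand. But a coordinator who reads the sections together finds three explicit statements that counts are unannounced against one incidental clause in a privacy section. An added sentence would only record an intention that is already clear. Although hair levels cannot repair a pill count, they are planned at each time point and do not depend on leftover pills, so they give an independent view of adherence.

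A sensitivity analysis that leaves out re-prompted or rescheduled counts is not a clear gain. It selects on behaviour after randomisation: people who are hard to reach or lack privacy may adhere differently, so the exclusion could bring in a selection bias of its own.

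**Conclusion.** No change to the plan is needed. The f.2.b sentence is a loosely worded confidentiality rule, and the protocol's operational sections already settle that the monthly counts come without warning. What is missing is detail on message timing, which staff can fill sensibly by sending the coded message, or making the call, as the prompt for the count itself.

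The reductions to 6.5, 5.0 or 3.6 points rest wholly on assumed discarding shares. They also take the pilot counts as true adherence, although the protocol says those counts were open to dumping, they apply discarding to every count, and they use a usual-care control in place of EP. Both arms follow the same procedure, and a bias in favour of one arm would need different discarding by arm, which the documents do not show. Self report, hair drug levels (H2) and the laboratory outcomes (H3) do not depend on notice of a pill count. The conclusion would change only if counts were in practice announced in advance, and nothing in the documents shows such a plan.
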